Appendix 6. Sample Storage and Destruction

Any blood, pharmacokinetic (PK), anti-drug antibody, or biomarker sample collected according to the Schedule of Activities ([Table 2-1](#)) can be analyzed for any of the tests outlined in the protocol and for any tests necessary to minimize risks to study subjects. This includes testing to ensure analytical methods produce reliable and valid data throughout the course of the study. This can also include, but is not limited to, investigation of unexpected results, incurred sample reanalysis, and analyses for method transfer and comparability.

All samples and associated results will be coded prior to being shipped from the site for analysis or storage. Samples will be tracked using a unique identifier that is assigned to the samples for the study. Results are stored in a secure database to ensure confidentiality.

If informed consent is provided by the subject, Amgen can do additional testing on remaining samples (ie, residual and back-up) to investigate and better understand the osteoporosis, the dose response and/or prediction of response to romosozumab, characterize antibody response, and characterize aspects of the molecule (eg, mechanism of action/target, metabolites). Results from this analysis are to be documented and maintained, but are not necessarily reported as part of this study. Samples can be retained for up to 20 years.

Since the evaluations are not expected to benefit the subject directly or to alter the treatment course, the results of pharmacogenetic, biomarker development, or other exploratory studies are not placed in the subject's medical record and are not to be made available to the subject, members of the family, the personal physician, or other third parties, except as specified in the informed consent.

The subject retains the right to request that the sample material be destroyed by contacting the investigator. Following the request from the subject, the investigator is to provide the sponsor with the required study and subject number so that any remaining samples and any other components from the cells can be located and destroyed. Samples will be destroyed once all protocol-defined procedures are completed. However, information collected from samples prior to the request for destruction, will be retained by Amgen.

The sponsor is the exclusive owner of any data, discoveries, or derivative materials from the sample materials and is responsible for the destruction of the sample(s) at the

request of the subject through the investigator, at the end of the storage period, or as appropriate (eg, the scientific rationale for experimentation with a certain sample type no longer justifies keeping the sample). If a commercial product is developed from this research project, the sponsor owns the commercial product. The subject has no commercial rights to such product and has no commercial rights to the data, information, discoveries, or derivative materials gained or produced from the sample. See [Appendix 3](#) for subject confidentiality.

Appendix 7. Hepatotoxicity Stopping Rules: Suggested Actions and Follow-up Assessments and Study Treatment Rechallenge Guidelines

Subjects with abnormal hepatic laboratory values (ie, alkaline phosphatase [ALP], aspartate aminotransferase [AST], alanine aminotransferase [ALT], total bilirubin [TBL]) and/or international normalized ratio (INR) and/or signs/symptoms of hepatitis (as described below) may meet the criteria for withholding or permanent discontinuation of Amgen investigational product or other protocol-required therapies, as specified in the *Guidance for Industry Drug-Induced Liver Injury: Premarketing Clinical Evaluation, July 2009*.

Criteria for Withholding and/or Permanent Discontinuation of Amgen Investigational Product and Other Protocol-required Therapies Due to Potential Hepatotoxicity

The following stopping and/or withholding rules apply to subjects for whom another cause of their changes in liver biomarkers (TBL, INR, and transaminases) has not been identified.

Important alternative causes for elevated AST/ALT and/or TBL values include, but are not limited to:

- Hepatobiliary tract disease
- Viral hepatitis (eg, hepatitis A/B/C/D/E, Epstein-Barr Virus, cytomegalovirus, herpes simplex virus, varicella, toxoplasmosis, and parvovirus)
- Right sided heart failure, hypotension or any cause of hypoxia to the liver causing ischemia
- Exposure to hepatotoxic agents/drugs or hepatotoxins, including herbal and dietary supplements, plants and mushrooms
- Heritable disorders causing impaired glucuronidation (eg, Gilbert's syndrome, Crigler-Najjar syndrome) and drugs that inhibit bilirubin glucuronidation (eg, indinavir, atazanavir)
- Alpha-1 antitrypsin deficiency
- Alcoholic hepatitis
- Autoimmune hepatitis
- Wilson's disease and hemochromatosis
- Nonalcoholic fatty liver disease including steatohepatitis (NASH)
- Non-hepatic causes (eg, rhabdomyolysis, hemolysis)

If investigational product(s) is/are withheld, the subject is to be followed for possible DILI according to recommendations in the last section of this appendix.

Rechallenge may be considered if an alternative cause for impaired liver tests (ALT, AST, ALP) and/or elevated TBL, is discovered and the laboratory abnormalities resolve to normal or baseline (see next section in this appendix).

Table 12-2. Conditions for Withholding and/or Permanent Discontinuation of Amgen Investigational Product and Other Protocol-required Therapies Due to Potential Hepatotoxicity

Analyte	Temporary Withholding	Permanent Discontinuation
TBL	> 3x ULN at any time	> 2x ULN
		OR
INR	--	> 1.5x ULN (for subjects not on anticoagulation therapy)
	OR	AND
AST/ALT	> 8x ULN at any time > 5x ULN but < 8x ULN for ≥ 2 weeks > 5x ULN but < 8x ULN and unable to adhere to enhanced monitoring schedule > 3x ULN with clinical signs or symptoms that are consistent with hepatitis (such as right upper quadrant pain/tenderness, fever, nausea, vomiting, and jaundice)	In the presence of no important alternative causes for elevated AST/ALT and/or TBL values > 3x ULN (when baseline was < ULN)
	OR	
ALP	> 8x ULN at any time	--

ALP = alkaline phosphatase; ALT = alanine aminotransferase; AST = aspartate aminotransferase; INR = international normalized ratio; TBL = total bilirubin; ULN = upper limit of normal

Criteria for Rechallenge of Amgen Investigational Product and Other Protocol-required Therapies After Potential Hepatotoxicity

The decision to rechallenge the subject is to be discussed and agreed upon unanimously by the subject, investigator, and Amgen.

If signs or symptoms recur with rechallenge, then romosozumab is to be permanently discontinued. Subjects who clearly meet the criteria for permanent discontinuation (as described in [Table 12-2](#)) are never to be rechallenged.

Drug-induced Liver Injury Reporting and Additional Assessments

Reporting

To facilitate appropriate monitoring for signals of DILI, cases of concurrent AST or ALT and TBL and/or INR elevation, according to the criteria specified in the above, require the following:

- The event is to be reported to Amgen as a serious adverse event within 24 hours of discovery or notification of the event (ie, before additional etiologic investigations have been concluded)
- The appropriate CRF (eg, Event CRF) that captures information necessary to facilitate the evaluation of treatment-emergent liver abnormalities is to be completed and sent to Amgen

Other events of hepatotoxicity and potential DILI are to be reported as serious adverse events if they meet the criteria for a serious adverse event defined in [Appendix 4](#).

Additional Clinical Assessments and Observation

All subjects in whom investigational product(s) or protocol-required therapies is/are withheld (either permanently or conditionally) due to potential DILI as specified in [Table 12-2](#) or who experience AST or ALT elevations > 3x upper limit of normal (ULN) are to undergo a period of “close observation” until abnormalities return to normal or to the subject’s baseline levels.

Assessments that are to be performed during this period include:

- Repeat AST, ALT, ALP, bilirubin (total and direct), and INR within 24 to 48 hours
- In cases of TBL > 2x ULN or AST/ALT much greater than 3x ULN, retesting should be performed within 24 hours; subjects should be monitored at least twice weekly.

Testing frequency of the above laboratory tests may decrease if the abnormalities stabilize or the investigational product(s) or protocol-required therapies has/have been discontinued AND the subject is asymptomatic.

Initiate investigation of alternative causes for elevated AST or ALT and/or elevated TBL.

The following are to be considered depending on the clinical situation:

- PT/INR, fractionated bilirubin, and any other potentially relevant laboratory evaluations of liver function or disease
- Complete blood count (CBC) with differential to assess for eosinophilia

- A more detailed history of:
 - Prior and/or concurrent diseases or illness
 - Exposure to environmental and/or industrial chemical agents
 - Symptoms (if applicable) including right upper quadrant pain, hypersensitivity-type reactions, fatigue, nausea, vomiting, and fever
 - Prior and/or concurrent use of alcohol, recreational drugs, and special diets
 - Concomitant use of medications (including non-prescription medicines and herbal and dietary supplements), plants, and mushrooms
- Full viral and autoimmune hepatitis evaluation (serologies for hepatitis A, B, C, D, E, Epstein-Barr Virus, Herpes Simplex Virus, etc.); evaluate for other potential causes of DILI, including but not limited to: Nonalcoholic Steatohepatitis, hypoxic/ischemic hepatopathy, and biliary tract disease
- Creatine phosphokinase (CPK), haptoglobin, lactate dehydrogenase (LDH), and peripheral blood smear
- Appropriate liver imaging or biopsy if clinically indicated; strongly consider these tests in cases of concurrent transaminase and TBL elevation that require permanent withholding of investigational product
- Appropriate blood sampling for pharmacokinetic analysis if this has not already been collected
- Gastroenterology or hepatology consult

Follow the subject and the laboratory tests (ALT, AST, TBL, INR) until all laboratory abnormalities return to baseline or normal or considered stable by the investigator. The “close observation period” is to continue for a minimum of 4 weeks after discontinuation of all investigational product(s) and protocol-required therapies.

The potential DILI event and additional information such as medical history, concomitant medications and laboratory results must be captured in the corresponding CRFs.

The purpose of this Statistical Analysis Plan is to provide details of the statistical analyses that have been outlined within the protocol for Study 20150120, Romosozumab dated 10 August 2017. The scope of this plan includes the primary analysis and the final analysis that are planned and will be executed by the Amgen Global Biostatistical Science department unless otherwise specified.

2. Objectives, Endpoints and Hypotheses

2.1 Objectives and Endpoints

Objectives	Endpoints
Primary	

To evaluate the noninferiority of a 6-month treatment with 210 mg romosozumab at 90 mg/mL administered subcutaneously (SC) once a month (QM) in postmenopausal women with osteoporosis either by healthcare provider (HCP) administration with prefilled syringe (PFS) or by subject self-administration with autoinjector/pen (AI/Pen)	
Percent change from baseline in bone mineral density (BMD) at the lumbar spine, as assessed by dual-energy x-ray absorptiometry (DXA)
Secondary	
Efficacy 
To evaluate the efficacy of a 6-month treatment with 210 mg romosozumab at 90 mg/mL SC QM in postmenopausal women with osteoporosis either by HCP administration with PFS or by subject self-administration with AI/Pen	
Percent changes from baseline in BMD at the total hip and femoral neck by DXA
Safety 
To evaluate the safety and tolerability of a 6-month treatment with 210 mg romosozumab at 90 mg/mL SC QM by HCP administration with PFS or by subject self-administration with AI/Pen	
Subject incidence of treatment-emergent adverse events, serious adverse events, and adverse device effectsSubject incidence of developing anti-romosozumab antibodiesChange from baseline in laboratory assessments and vital signs

Objectives	Endpoints
Exploratory	

2.2 Hypotheses and/or Estimations

The primary hypothesis is that the mean percent change from baseline in lumbar spine DXA BMD at Month 6 in subjects (postmenopausal women with osteoporosis) self-administering 210 mg romosozumab QM with AI/Pen is not inferior to that in subjects receiving 210 mg romosozumab QM by HCP administration with PFS using a margin of -2 percentage points. It is hypothesized that the mean percent change from baseline in lumbar spine DXA BMD at Month 6 in subjects who self-administer 210 mg romosozumab QM with AI/Pen is the same as that in subjects who receive 210 mg romosozumab QM by HCP administration with PFS.

3. Study Overview

3.1 Study Design

This is a phase 3 randomized, multicenter, open-label, noninferiority study of romosozumab in postmenopausal women with osteoporosis. The study is designed to evaluate the noninferiority of a 6-month 210 mg romosozumab SC QM treatment by subject self-administration with AI/Pen to HCP administration with PFS.

After signing the informed consent form, subjects will undergo the following periods:

- Screening period (35 days) to complete eligibility assessments
- Open-label treatment period (6 months)
- Follow-up period (3 months)

[figure not shown]
During the open-label treatment period, subjects will be randomized to receive romosozumab either via HCP administration with PFS or via self-administration with AI/Pen.

During the follow-up period, subjects will be followed for an additional 3 months to ensure appropriate follow-up for anti-romosozumab antibody formation and adverse events.

The primary analysis will be performed after all subjects have had the opportunity to complete the Month 6 visit. The final analysis will be performed after all subjects have had the opportunity to complete the Month 9 visit.

3.2 Sample Size

The noninferiority margin is calculated on the basis of the comparison of 210 mg romosozumab at a 90 mg/mL concentration administered QM by an HCP using PFS with placebo on percent change from baseline in lumbar spine at Month 6 in postmenopausal women with low bone mass (Study 20120156).

[REDACTED]

[REDACTED]

[REDACTED]

[REDACTED]

[REDACTED] This result assumes a 5% dropout rate during the 6-month treatment period, no expected difference in mean percent changes in lumbar spine DXA BMD from baseline at Month 6 between the 2 groups, and a common standard deviation of 4.3 percentage points.

4. Covariates and Subgroups

4.1 Planned Covariates

All analyses assessing treatment effect of BMD will include randomized treatment, baseline BMD at the same body site as the endpoint, machine type, and interaction between baseline BMD and machine type as prognostic variables in the model.

4.2 Subgroups

No subgroups will be evaluated in this study.

5. Definitions

5.1 Basic Definitions

Investigational Product (IP)

Romosozumab 210 mg QM

Interactive Voice Response System (IVRS)

The system used to assign eligible subjects to randomized treatment as well as to manage IP supply at the site and track subjects' study termination data.

Treatment-emergent Adverse Events

Adverse Events (AEs) starting on or after first dose of investigational product as determined by the flag indicating if the adverse event started prior to the first dose on the Adverse Events Summary CRF and up to the end of study date.

Serious adverse events (SAEs) starting on or after first dose of investigational product as determined by the flag indicating if the adverse event started prior to the first dose on the Adverse Events Summary CRF and up to the end of study date.

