8.2 Discontinuation From the Study

Withdrawal of consent for a study means that the subject does not wish to receive further protocol-required therapies or procedures, and the subject does not wish to or is unable to continue further study participation. Subject data up to withdrawal of consent will be included in the analysis of the study, and where permitted, publicly available data can be included after withdrawal of consent. The investigator is to discuss with the

subject appropriate procedures for withdrawal from the study, and must document the subject's decision to withdraw in the subject's medical records.

If a subject withdraws from the study, he/she may request destruction of any samples taken and not tested, and the investigator must notify Amgen accordingly (see [Appendix 6](#) for further details). Refer to the [Schedule of Activities](#) for data to be collected at the time of study discontinuation and follow-up and for any further evaluations that need to be completed.

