8.3 Lost to Follow-up

A subject will be considered lost to follow-up if he or she repeatedly fails to return for scheduled visits and is unable to be contacted by the study site.

The following actions must be taken if a subject fails to return to the clinic for a required study visit:

- The site must attempt to contact the subject and reschedule the missed visit as soon as possible and counsel the subject on the importance of maintaining the assigned visit schedule and ascertain whether or not the subject wishes to and/or is able to continue in the study.
- In cases in which the subject is deemed lost to follow-up, the investigator or designee must make every effort to regain contact with the subject (where possible, 3 telephone calls and, if necessary, a certified letter to the subject's last known mailing address or local equivalent methods). These contact attempts are to be documented in the subject's medical record.
- If the subject continues to be unreachable, he/she will be considered to have withdrawn from the study with a primary reason of lost to follow-up.
- For subjects who are lost to follow-up, the investigator can search publicly available records [where permitted] to ascertain survival status. This ensures that the data set(s) produced as an outcome of the study is/are as comprehensive as possible.

9. Study Assessments and Procedures

Study procedures and their time points are summarized in the Schedule of Activities (see [Table 2-1](#)).

As protocol waivers or exemptions are not allowed if an enrolled subject is subsequently determined to be ineligible for the study, this must be discussed with the sponsor immediately upon occurrence or awareness to determine if the subject is to continue or discontinue study treatment.

Adherence to the study design requirements, including those specified in the Schedule of Activities, is essential and required for study conduct.

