9.1.3 Safety Follow-up

Upon permanent discontinuation from the study treatment for any reason, a safety follow-up visit will be performed approximately 30 (+3) days after the end of the last dosing interval of investigational product.

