9.2.3.1 Adverse Events

9.2.3.1.1 Time Period and Frequency for Collecting and Reporting Safety Event Information

9.2.3.1.1.1 Disease-related Events

Disease-related events are defined in [Appendix 4](#).

The investigator is responsible for ensuring that all disease-related events observed by the investigator or reported by the subject that occur after the first dose of investigational product(s)/study treatment/protocol-required therapies through EOS are reported using the Event CRF.

Disease-related events assessed by the investigator to be more severe than expected and/or related to the investigational product(s)/study treatment/protocol-required therapies, and determined to be serious, must be reported on the Event CRF as serious adverse events.

Disease-related events pre-defined for this study include: fractures (serious or non-serious), as they are anticipated to occur in the study population due to the underlying disease.

9.2.3.1.1.2 Adverse Events

The adverse event grading scale to be used for this study will be the Common Terminology Criteria for Adverse Events (CTCAE) and is described in [Appendix 4](#).

The investigator is responsible for ensuring that all adverse events observed by the investigator or reported by the subject that occur after first dose of investigational product(s) through EOS are reported using the Event CRF.

9.2.3.1.1.3 Serious Adverse Events

The investigator is responsible for ensuring that all serious adverse events observed by the investigator or reported by the subject that occur after signing of the informed consent through EOS, ET, or 30 days after the last dose of investigational product (whichever is longer) are reported using the Event CRF.

All serious adverse events will be collected, recorded and reported to the sponsor or designee within 24 hours, as indicated in [Appendix 4](#). The investigator will submit any updated serious adverse event data to the sponsor within 24 hours of it being available.

The criteria for grade 4 in the CTCAE grading scale differs from the regulatory criteria for serious adverse events. It is left to the investigator's judgment to report these grade 4 abnormalities as serious adverse events.

9.2.3.1.1.4 Adverse Events and Serious Adverse Events Requiring Adjudication

The following events will be submitted to independent committees for adjudication:

- potential ONJ events
- potential cases of AFF

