5.3 Study Dates

Enrollment (Randomization) Date

The date on which a subject is assigned to one of the treatments through IVRS.

First Dose Date

The date of administration of the first dose of IP; this may or may not be the same as the randomization date.

Last Dose Date

The date of administration of last dose of IP

Study Day 1

Study day 1 is defined as the first dose date. For subjects who did not receive IP, study day 1 is defined as the randomization date.

End of the 6-Month Treatment Period Date

The end of the 6-month treatment period date is defined as the date of the last assessment at the Month 6 visit. For subjects who discontinue from the study before completing the Month 6 visit, the end of study date is used for the end of the 6-month treatment period end date. For those subjects who missed the Month 6 visit but did not terminate the study early, the target day (Day 183) for Month 6 plus 3 days will be used as the end of the 6-month treatment period date.

Start of the Follow-up Period Date

The start of the follow-up period date is defined as the end of the 6-month treatment period date plus one day.

End of the Follow-up Period Date

For subjects with non-missing start of the follow-up period date, the end of the follow-up period date is defined as the end of study date as recorded on the electronic case report form (CRF).

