9.7 Other Analyses

9.7.1 Analyses of Pharmacokinetic or Pharmacokinetic/Pharmacodynamic Endpoints

Individual and mean serum romosozumab concentration-time data will be tabulated and presented graphically using nominal times. Descriptive statistics will be provided for romosozumab serum concentrations at each time point. The data set will be analyzed using the current version of Phoenix WinNonlin within the Pharsight Knowledgebase System data repository. Romosozumab serum concentrations with values below the lower limit of quantification will be set to zero for analysis. Reasons for excluding any data from the pharmacokinetic analyses will be provided. These analyses will be performed by the Clinical Pharmacology Modeling and Simulation group.

10. Changes From Protocol-specified Analyses

Table 10-1 of protocol version 1.0 dated 10 August 2017 states that the non-inferiority margin is based on the treatment difference:

$$(\mu_{\text{romosozumab HCP PFS}} - \mu_{\text{romosozumab self-administration AI/Pen}}).$$

However, the noninferiority margin will be based on:

$$(\mu_{\text{romosozumab self-administration AI/Pen}} - \mu_{\text{romosozumab HCP PFS}})$$

This is reflected in Table 3-1 of this statistical analysis plan and in [Section 7.2](#).

According to the Schedule of Activities in Protocol version 1.0 (Table 2-1) physical measurements (height and weight) will be assessed at baseline, month 3, and month 6. However, physical measurements at month 3 were not collected. Therefore, summaries of physical measurements will not include month 3.

11. Literature Citations / References

Van Elteren P.H. (1960) On the combination of independent two-sample test of Wilcoxon, Bulletin of the International Statistical Institute, 37, 351-361.

12. Appendices

Appendix A. Technical Detail and Supplemental Information Regarding Statistical Procedures and Programs

For the baseline assessment (excluding DXA), regardless of the width of the visit window, if there are multiple records within a Baseline window, the record that is the closest to and on or prior to Study Day 1 will be considered as the baseline value.

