9.6.1 Adverse Events and Disease-related Events

Replace:

The Medical Dictionary for Regulatory Activities (MedDRA) version 20.1 or later will be used to code all events categorized as adverse events and disease-related events to a system organ class and a preferred term.

Treatment-emergent adverse events are events with an onset after the administration of the first dose of investigational product.

The subject incidence of adverse events will be summarized for all treatment-emergent adverse events, serious adverse events, adverse events leading to withdrawal of investigational product, fatal adverse events, and adverse events of interest. Events of interest are described in Section 9.6.1.1.

Subject incidence of all treatment-emergent adverse events, serious adverse events, adverse events leading to withdrawal of investigational product, and fatal adverse events will be tabulated by system organ class and preferred term in descending order of frequency.

In addition, summaries of treatment-emergent and serious adverse events occurring in at least 5% of the subjects and serious adverse events occurring in at least 2% of the subjects by preferred term in any treatment arm will be provided in descending order of frequency.

Summaries of treatment-emergent and serious adverse events will be tabulated by system organ class, preferred term, and grade.

Subject incidence of disease-related events will be summarized for all treatment-emergent disease-related events and fatal disease-related events. Adverse device effects will also be summarized.

The subject incidence of treatment-emergent adverse events and adverse device effects will be summarized by actual treatment received.

With:

The Medical Dictionary for Regulatory Activities (MedDRA) version 22.0 or later will be used to code all events categorized as adverse events and disease-related events to a system organ class and a preferred term.

Treatment-emergent adverse events are events with an onset on or after the

administration of the first dose of investigational product and will include events reported as disease-related events.

The subject incidence of adverse events will be summarized for all treatment-emergent adverse events, serious adverse events, adverse events leading to withdrawal of investigational product, fatal adverse events, and adverse events of interest. Events of interest are described in Section 9.6.1.1.

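### Should the SAP's treatment-emergent SAE window run to 30 days after the last dose, as the protocol's SAE reporting period does?

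*SAP*

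**What the plan says.** SAP 5.1 defines treatment-emergent events in two paragraphs with the same ending, one for adverse events and one for SAEs. Events count if they start on or after the first dose, judged by a flag for whether the event "started prior to the first dose on the Adverse Events Summary CRF and up to the end of study date". SAP 5.3 treats the end of study date as a subject-level date taken from the electronic CRF.

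The replacement text for SAP 9.6.1 in SAP Amendment 1 describes treatment-emergent events as having an onset on or after "administration of the first dose of investigational product and will include events reported as disease-related events". It gives no end point.

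Protocol 9.2.3.1.1.3 covers the reporting of SAEs. Those that occur from consent "through EOS, ET, or 30 days after the last dose of investigational product (whichever is longer) are reported using the Event CRF". Protocol 9.2.3.1.1.2 collects other adverse events from the first dose through EOS, which agrees with SAP 5.1.

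Three further protocol provisions bear on women who leave early:

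- Section 9.1.3: after permanent discontinuation of treatment, "a safety follow-up visit will be performed approximately 30 (+3) days after the end of the last dosing interval of investigational product".
- Section 8.2: data up to withdrawal of consent enter the analysis and, beyond that, "where permitted, publicly available data can be included after withdrawal of consent".
- Section 8.3: for women lost to follow-up, "the investigator can search publicly available records [where permitted] to ascertain survival status".

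**The concern.** The protocol gives SAEs a longer limit than other adverse events, and SAP 5.1 does not carry that limit into the analysis. Its separate SAE paragraph simply repeats the ending used for adverse events. SAP 9.6.1 restates the definition without any end, so a programmer reading that section alone might apply no cut-off.

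Suppose a woman withdraws a few days after a dose and public records show that she died on day 20 after that dose. The death lies inside the protocol's reporting period and outside the SAP 5.1 window. An error of this kind can only remove SAEs and deaths from the tables. Comparing safety and tolerability is the primary objective of the final analysis (SAP 7.3), and SAP Section 10, which lists departures from the protocol, does not mention the difference.

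**Working it through.** The plan states no figure to reproduce. The questions are who can fall between the two limits and how many events that could involve.

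**1. Do the passages conflict?** Protocol 9.2.3.1.1.3 starts at consent and says what investigators must report. The protocol uses the term treatment-emergent but never defines it, and its safety analysis text (10.3.2.3.1) sets no window. SAP 5.1 therefore does not override a protocol-specified analysis, and nothing is missing from SAP Section 10. SAP 9.6.1 is silent on the end, and SAP 5.1, the definitions section, supplies it. That is incomplete wording; the two sections do not give different answers.

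**2. Completers.** The last planned dose is at Month 5 and EOS is Month 9 (-7/+3 days) (Protocol Table 2-1). Doses may be given up to 14 days from target (7.4.1.1), and months are calendar months (9.1.2). Over all start dates in a year:

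| Event | Study day |
|---|---|
| Month 5 target | 151 to 154 |
| Month 5 dose + 30 days | 181 to 184 |
| Month 5 dose 14 days late + 30 days | 195 to 198 |
| Earliest in-window Month 9 visit (274 to 277, less 7) | 267 to 270 |

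Matched by start date, EOS follows the 30-day limit by 83 to 86 days, or by 69 to 72 days after a late dose. The 30-day limit never applies to completers.

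**3. Women who attend the Section 9.1.3 visit.** A dosing interval of about 30 to 31 days plus 30 to 33 days puts that visit about 60 to 64 days after the last dose. Protocol Appendix 1 defines a subject's end of study as the last day of protocol-specified procedures. If the CRF date follows that definition, the 30 days are covered.

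**4. Women lost to follow-up.** Section 8.3 requires repeated failure to return. Two missed monthly visits fall about 61 days after the target date of the last dose, or about 61 - 14 = 47 days after a dose given 14 days late. The 30-day limit has passed by then, unless the CRF back-dates the end of study date to the last contact. The documents do not state which convention applies.

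**5. Size for those who remain.** With the end of study date t days after the last dose (t not negative), the uncovered time is max(0, 30 - t): 30 days at t = 0, 16 at t = 14, none from t = 30.

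- Women: 260 × 5% = 13. N is from Protocol 5.2 and dropout from Protocol 10.1.
- Departures spread evenly over days 0 to 30 give a mean of 15 days. 13 × 15 = 195 person-days = 195/365.25 = 0.534 person-years.
- Total follow-up: (247 × 275 + 13 × 92)/365.25 = 189 person-years, assuming that leavers average 92 days. Share uncovered: 0.534/189 = 0.28%.
- The documents give no SAE rate, so 5 to 20 per 100 person-years is assumed. Expected events: 0.534 × 0.05 = 0.027 to 0.534 × 0.20 = 0.107, both arms together.
- If half attend the safety visit: 97.5 person-days = 0.267 person-years, giving 0.013 to 0.053 events.
- Extreme case, all 13 leaving on the dose day: 13 × 30 = 390 person-days = 1.07 person-years, about 0.6% of follow-up, giving 0.05 to 0.21 events.

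One event in a 130-subject arm is 1/130 = 0.77 percentage points.

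**The case for a change.** The strongest argument for a change is that the gap exists on the page, works in one direction only and would be cheap to close, since SAP 5.3 already defines the last dose date. In the PFS arm the injection is the last procedure of a visit. If the CRF records last contact as the end of study date, a woman who never returns would have an end of study date equal to her last dose date, with the full 30 days uncovered. Sections 8.2 and 8.3 of the protocol show that information on such women is expected in some cases. A single death matters clinically even when the expected count is small.

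The possibility stands: an SAE can be reportable and still outside SAP 5.1. The argument for acting on it is weaker.

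- For women who withdraw consent, Protocol 8.2 takes their data up to withdrawal into the analysis, which broadly matches the SAP cut-off. Only public data remain, where permitted, and these mainly show survival. The relevant rate is then a death rate, which is lower than the all-SAE rate used above.
- Such an event would not disappear. Within the reporting period it goes on the Event CRF, and all deaths go to adjudication. The summary of adjudicated cardiovascular events in SAP 9.6.1.1.4 states no end-of-study cut-off.
- Both arms receive the same drug and dose, and nothing in the documents points to a difference between arms.
- Extending the window is less simple than it looks. SAP 7.2 limits the primary analysis to treatment-period data, and SAP 5.3 ends that period at the end of study date for early leavers. A longer window in 5.1 alone would make the same event both included and excluded at the primary analysis. In the AI/Pen arm the last dose date may itself be imputed from the dispensing date (SAP Table 8-2), so the limit would be less exact there.

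**Conclusion.** No change to the plan follows. SAP 5.1 and the protocol's SAE reporting period do end at different points, but the difference touches only women whose end of study date is less than 30 days after a dose. That is at most about 13 of 260 women at the planned 5% dropout, and fewer once those who attend the safety visit are set aside. The expected number of excluded events is 0.03 to 0.11 over both arms, and about 0.2 if every dropout left on a dosing day. These figures rest on the planned dropout, an assumed 5 to 20 SAEs per 100 person-years, full ascertainment after departure, and an end of study date no earlier than the last dose. Depending on how the CRF sets that date, the gap may already be closed.

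The safety analyses are descriptive without formal testing, and the noninferiority comparison of lumbar spine BMD is untouched. What remains is a definitional nicety: SAP 9.6.1 can be read with 5.1, and an SAE that starts after the end of study date can be described individually if one occurs. Aligning the wording would alter no result or conclusion.
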